## **10.0 CTM INFORMATION & ADVERSE EVENTS MANAGEMENT**

### **10.1 Rucaparib (CO-338/AG-014699/PF-01367388)**

#### **10.1.1 Mechanism of Action: Inhibits PARP**

**10.1.2 Availability:** IV drug will be provide by Clovis via the Hoosier Oncology Group. rucaparib investigational drug product will be supplied as rucaparib Lyophilized Powder for Injection, 12 mg/vial (as free base), in 10 mL/20 mm, Type I amber glass vials. The composition of rucaparib drug product consists of rucaparib (phosphate salt), mannitol, water for injection (WFI), and nitrogen. The resulting drug product is an off-white to yellow cake.

**Availability:** Oral drug will be provide by Clovis via the Hoosier Oncology Group. rucaparib investigational drug product will be supplied as rucaparib immediate release, film coated tablets, 40 mg and 60 mg (as free base), in HDPE containers with child resistant closures. The composition of rucaparib drug product consists of rucaparib (camsylate salt), microcrystalline cellulose, sodium starch glycolate, dicalcium phosphate, and magnesium stearate. The cosmetic white film coating, Opadry II, contains HPMC 2910, hypromellose 6cP, macrogol/PEG3350, triacetin, titanium dioxide, and lactose monohydrate. 40 mg rucaparib tablets are 9.5 mm round convex in shape, while 60 mg tablets are 15.4 mm x 8 mm oval in shape.

**10.1.3** Storage and Reconstitution: Vials of rucaparib Lyophilized Powder for Injection, 12 mg/vial (as free base), must be stored at room temperature (15°C to 30°C) and protected from light.

Each rucaparib drug product vial is to be reconstituted with 6 mL sterile WFI to yield a 2 mg/mL (as free base) clear yellow solution. Once 6 mL of SWFI is injected into the vial through the stopper, vigorously shake the vial for at least 30 seconds to allow complete drug dissolution in the vial. The reconstituted solution should be clear and free of particles. Segregate and store any rejected vials separately at controlled room temperature (15 to 30°C) and notify sponsor immediately. The reconstituted rucaparib drug product must be used within 24 hours and stored at controlled room temperature (15°C to 30°C). Do not refrigerate reconstituted product.

Bottles of rucaparib 40 mg and 60 mg (as free base) immediate release film coated tablets, must be stored at room temperature (15°C to 30°C)

**10.1.4** IV administration: The reconstituted solution will be mixed in an infusion bag containing D5W. Drug should be administered as listed in table 1 of the protocol, as an intravenous infusion. Infusion equipment including infusion bags and tubing must be compatible with rucaparib. Products meeting compatibility requirements will be listed in the study documentation prior to the enrollment of the first patient.

Chemotherapy will be administered approximately one hour after the end of rucaparib administration.

Oral administration: Patients should take rucaparib fasting (at least 1 hour *before* OR at least 2 hours *after* eating)

**10.1.5** Side Effects:

In general rucaparib has been well tolerated in early clinical trials; dose limiting toxicity has not been identified at doses that effectively inhibit PARP. Most adverse events were reversible and short in duration. Most hematologic toxicity was related to concurrently administered chemotherapy and was not obviously increased with combined therapy. No cardiac toxicity (changes in electrocardiogram or left ventricular ejection fraction) with repeated dosing. The main adverse event associated only with rucaparib is mild injection site reaction.

~~ADD ORAL here if needed~~

**10.2** **Cisplatin Other: Platinol (NSC-119875); Cis-diamminedichloroplatinum**

**10.2.1** Classification: Alkylating agent

**10.2.2** Action:

Cisplatin forms covalent bonds with nucleophilic sites on guanine present in all DNA. As cisplatin is a bifunctional agent, it is able to bind to 2 sites in a DNA strand. This results in the formation of inter- and intra- chain cross-linkings, which interferes with cellular transcription and replication. Regulatory mechanisms detect the abnormal DNA and so

activate a chain of responses to try and correct it. This, ultimately, causes cell death (apoptosis).

**10.2.3 Availability:**

Cisplatin is commercially available.

**10.2.4 Storage:**

Cisplatin Injection is a sterile, multi-dose vial without preservatives. Store at 15° to 25°C (59° to 77°F). **Note:** Do not refrigerate. Protect unopened container from light. The cisplatin remaining in the amber vial following initial entry is stable for 28 days protected from light or for 7 days under fluorescent room light.

**10.2.5 Reconstitution:**

The aqueous solution should be used intravenously only and should be administered by IV. Cisplatin is a cytotoxic chemotherapeutic agent. Appropriate precautions for hazardous drug handling should be taken during handling, preparation, administration and disposal of this agent. As with other potentially toxic compounds, caution should be exercised in handling the aqueous solution. Skin reactions associated with accidental exposure to cisplatin may occur. The use of gloves is recommended. If cisplatin contacts the skin or mucosa, immediately and thoroughly wash the skin with soap and water and flush the mucosa with water.

**10.2.6 Administration:**

Cisplatin will be administered IV according to institutional guidelines.

Hydration for cisplatin can be administered at the discretion of the treating physician and according to institutional standards. However, the following regimen is suggested:

**Table 10: Pre-dose: Hydration guidelines**

	Instructions
Normal Saline	at 350 mL/hour x 1000 mL
Mannitol bolus, immediately prior to cisplatin	12.5 g IV piggyback in 25 mL D5W x1 through 1.2 micron in-line filter

**Table 11: Post-dose: Hydration guidelines**

	Instructions
Normal Saline	at 350 mL/hour x 1000 mL

**10.2.7 Side Effects:**

**Nephrotoxicity:** Dose related and cumulative renal insufficiency is the major dose-limiting toxicity. Renal toxicity has been noted in 28-36% of patients treated with a single dose of 50 mg/m^2. It is first noted during the second week after a dose and is manifested by elevations in BUN and creatinine, serum uric acid, and/or a decrease in creatinine clearance.

Note: Renal toxicity becomes more prolonged and severe with repeated courses of the drug. Renal function must return to normal before another dose of cisplatin can be given.

**10.2.8 Ototoxicity:** Ototoxicity has been observed in up to 31% of patients treated with a single dose of cisplatin  $50 \text{ mg/m}^2$ , and is manifested by tinnitus and/or hearing loss in the high frequency range (4,000 to 8,000 Hz). Decreased ability to hear normal conversational tones may occur occasionally. Deafness after the initial dose of cisplatin has been reported rarely. Ototoxic effects may be more severe in children receiving cisplatin. Hearing loss can be unilateral or bilateral and tends to become more frequent and severe with repeated doses. Ototoxicity may be enhanced with prior or simultaneous cranial irradiation. It is unclear whether cisplatin-induced ototoxicity is reversible. Ototoxic effects may be related to the peak plasma concentration of cisplatin. Vestibular toxicity has also been reported. Ototoxicity may become more severe in patients being treated with other drugs with nephrotoxic potential. Patients should be questioned regarding any history of hearing deficit.

**10.2.9 Hematologic:** Myelosuppression occurs in 25% to 30% of patients treated with cisplatin. The nadirs in circulating platelets and leukocytes occur between days 18 to 23 (range 7.5 to 45) with most patients recovering by day 39 (range 13 to 62). Leukopenia and thrombocytopenia are more pronounced at higher doses ( $>50 \text{ mg/m}^2$ ). Anemia (decrease of 2 g hemoglobin/100 mL) occurs at approximately the same frequency and with the same timing as leukopenia and thrombocytopenia. Fever and infections have also been reported in patients with neutropenia. In addition to anemia secondary to myelosuppression, a Coombs' positive hemolytic anemia has been reported. In the presence of cisplatin hemolytic anemia, a further course of treatment may be accompanied by increased hemolysis, and this risk should be weighed by the Treating Physician.

The development of acute leukemia coincident with the use of cisplatin has rarely been reported in humans. In these reports, cisplatin was generally given in combination with other leukemogenic agents.

**10.2.10 Gastrointestinal:** Marked nausea and vomiting occur in almost all patients treated with cisplatin, and are occasionally so severe that the drug must be discontinued. Nausea and vomiting usually begin within 1 to 4 hours after treatment and last for 24 hours. Various degrees of vomiting, nausea and/or anorexia may persist for up to 1 week after treatment. Delayed nausea and vomiting (begins or persists 24 hours or more after chemotherapy) has occurred in patients attaining complete emetic control on the day of cisplatin therapy. Diarrhea has also been reported.

**10.2.11 Other Toxicities:** Vascular toxicities coincident with the use of cisplatin in combination with other antineoplastic agents have been reported rarely. The events are clinically heterogeneous and may include myocardial infarction, cerebrovascular accident, thrombotic microangiopathy (HUS), or cerebral arteritis. Various mechanisms have been proposed for these vascular complications. There are also reports of Raynaud's phenomenon occurring in patients treated with the combination of bleomycin, vinblastine with or without cisplatin. It has been suggested that hypomagnesemia developing coincident with the use of cisplatin may be an added, although not essential, factor associated with this event. However, it is currently unknown if the cause of Raynaud's phenomenon in these cases is the disease, underlying vascular compromise, bleomycin, vinblastine, hypomagnesemia, or a combination of any of these factors.

**10.2.12 Serum Electrolyte Disturbances:** Hypomagnesemia, hypocalcemia, hyponatremia, hypokalemia, and hypophosphatemia have been reported to occur in patients treated with cisplatin and are probably related to renal tubular damage. Tetany has occasionally been reported in those patients with hypocalcemia and hypomagnesemia. Generally, administering supplemental electrolytes and discontinuing cisplatin restore normal serum electrolyte levels. Inappropriate antidiuretic hormone syndrome has also been reported.

**10.2.13 Hyperuricemia:** Hyperuricemia has been reported to occur at approximately the same frequency as the increases in BUN and serum creatinine. It is more pronounced after doses greater than 50 mg/m^2, and peak levels of uric acid generally occur between 3 to 5 days after the dose. Allopurinol therapy for hyperuricemia effectively reduces uric acid levels.

**10.2.14 Neurotoxicity:** Neurotoxicity, usually characterized by peripheral neuropathies, has been reported. The neuropathies usually occur after prolonged therapy (4 to 7 months); however, neurologic symptoms have been reported to occur after a single dose. Although symptoms and signs of cisplatin neuropathy usually develop during treatment, symptoms of neuropathy may begin 3 to 8 weeks after the last dose of cisplatin, although this is rare. Cisplatin therapy should be discontinued when the symptoms are first observed. The neuropathy, however, may progress further even after stopping treatment. Preliminary evidence suggests peripheral neuropathy may be irreversible in some patients. Lhermitte's sign, dorsal column myelopathy, and autonomic neuropathy have also been reported. Loss of taste and seizures have also been reported. Muscle cramps, defined as localized, painful, involuntary skeletal muscle contractions of sudden onset and short duration, have been reported and were usually associated in patients receiving a relatively high cumulative dose of cisplatin and with a relatively advanced symptomatic stage of peripheral neuropathy.

**10.2.15 Ocular Toxicity:** Optic neuritis, papilledema, and cerebral blindness have been reported infrequently in patients receiving standard recommended doses of cisplatin. Improvement and/or total recovery usually occurs after discontinuing cisplatin. Steroids with or without mannitol have been used; however, efficacy has not been established.

**10.2.16 Blurred vision and altered color perception** have been reported after the use of regimens with higher doses of cisplatin or greater dose frequencies than those recommended in the package insert. The altered color perception manifests as a loss of color discrimination, particularly in the blue-yellow axis. The only finding on funduscopic exam is irregular retinal pigmentation of the macular area.

**10.2.17 Anaphylactic-like Reactions:** Anaphylactic-like reactions have been occasionally reported in patients previously exposed to cisplatin. The reactions consist of facial edema, wheezing, tachycardia, and hypotension within a few minutes of drug administration. Reactions may be controlled by IV epinephrine with corticosteroids and/or antihistamines as indicated. Patients receiving cisplatin should be observed carefully for possible anaphylactic-like reactions and supportive equipment and medication should be available to treat such a complication.

**10.2.18 Hepatotoxicity:** Transient elevations of liver enzymes, especially SGOT, as well as bilirubin, have been reported to be associated with cisplatin administration at the recommended doses.

**10.2.19 Other Events:** Other toxicities reported to occur infrequently are cardiac abnormalities, hiccups, elevated serum amylase, and rash. Alopecia, malaise, and asthenia have been reported as part of postmarketing surveillance.

Local soft tissue toxicity has rarely been reported following extravasation of cisplatin. Severity of the local tissue toxicity appears to be related to the concentration of the cisplatin solution. Infusion of solutions with a cisplatin concentration greater than 0.5 mg/mL may result in tissue cellulitis, fibrosis, and necrosis.

**10.2.20 Pregnancy:** Cisplatin can cause fetal harm when administered to a pregnant woman. Cisplatin is mutagenic in bacteria and produces chromosome aberrations in animal cells in tissue culture. In mice, cisplatin is teratogenic and embryotoxic. If this drug is used during pregnancy or if the patient becomes pregnant while taking this drug, the patient should be apprised of the potential hazard to the fetus. Patients should be advised to avoid becoming pregnant.

**10.2.21 Nursing Mothers:** Cisplatin has been reported to be found in human milk, patients receiving cisplatin should not breastfeed.

## 11.0 REPORTING ADVERSE EVENTS & SERIOUS ADVERSE EVENTS

### 11.1 Definitions of Adverse Events

#### 11.1.1 Adverse Event (AE)

Any untoward medical occurrence in a patient or clinical trial subject administered an investigational product and which does not necessarily have a causal relationship with the treatment. An adverse event (AE) can, therefore, be any unfavorable and unintended sign (including an abnormal finding), symptom, or disease temporally associated with the use of an investigational product, whether or not related to the investigational product.

#### 11.1.2 Serious Adverse Event (SAE)

A serious adverse event is any untoward medical occurrence resulting in one or more of the following:

- Results in death
- Is life-threatening (defined as an event in which the patient was at risk of death at the time of the event; it does not refer to an event which hypothetically might have caused death if it were more severe)
- Requires inpatient hospitalization or prolongation of existing hospitalization
- Results in persistent or significant disability/incapacity
- Is a congenital anomaly or birth defect
- Is an important medical event (defined as a medical event(s) that may not be immediately life-threatening or result in death or hospitalization but, based upon appropriate medical and scientific judgment, may jeopardize the patient or may require intervention (e.g., medical, surgical) to prevent one of the other serious outcomes listed in the definition above). Examples of such events include, but are not limited to, intensive treatment in an emergency room or at home for allergic

bronchospasm; blood dyscrasias or convulsions not resulting in hospitalization; or the development of drug dependency or drug abuse.

### **11.1.3 Unexpected Adverse Event**

An adverse event not mentioned in the Investigator's Brochure or package insert or the specificity or severity of which is not consistent with the Investigator's Brochure or package insert.

## **11.2 Adverse Event (AE) Reporting**

Adverse events (AEs) will be recorded from the time of consent and for at least 30 days after treatment discontinuation, regardless of whether or not the event(s) are considered related to trial medications. All AEs considered related to trial medication will be followed until resolution, return to baseline, or deemed clinically insignificant, even if this occurs post-trial.

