## 6.0 DOSE MODIFICATIONS

The NCI Common Terminology Criteria for Adverse Events (CTCAE) Version 3.0 will be used to grade adverse events.

Patients enrolled in this study will be evaluated clinically and with standard laboratory tests before and at regular intervals during their participation in this study as specified in section 7.0

Patients will be evaluated for adverse events (all grades), serious adverse events, and adverse events requiring study drug interruption or discontinuation at each study visit for the duration of their participation in the study.

Patients discontinued from the treatment phase of the study for any reason will be evaluated at least 30 days after the last dose of study drug.

Patients who require discontinuation of **rucaparib** due to adverse event, have a treatment interruption of > 21 days due to toxicity, or require a dose reduction below level 0, will be removed from the study.

Patients in the safety run-in, or Arm B, who require a cisplatin dose reduction below level -2, should proceed to **rucaparib** maintenance therapy.

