**Randomized Phase II – Arm A**

	Screening		Cycles 1-4	Post-treatment	Follow-up
	-30 days	-14 days	D1  (+/-3 days)	30-60 days from last treatment	+/-1 month
REQUIRED ASSESSMENTS					
Medical history	X				
Height	X				
Physical examination	X		X	X	X 
BP, weight	X		X	X	X 
ECOG performance status	X		X	X	X 
Blood Chemistries 		X	X	X	
Calculated creatinine clearance		X	X	X	
Platelets, ANC & Hgb		X	X	X	
Breast imaging					yearly
Electrocardiogram 	X		X		
MUGA or Echocardiogram	X				
Urine pregnancy or serum HCG 		X			
Adverse event and concomitant medication assessment	X		X	X	
TREATMENT					
Cisplatin			X		
CORRELATIVE STUDIES					
Tumor from diagnosis -Optional	X				
Tumor from definitive surgery -Mandatory	X				
Genomic DNA - Optional			X 		

1. Screening values obtained within 7 days of Day 1 do not need to be repeated prior to cycle 1 day 1.

2. Serum chemistries (creatinine, glucose, total protein, blood urea nitrogen [BUN], total carbon dioxide [CO2], albumin, total bilirubin, alkaline phosphatase, and aspartate transaminase [AST] and alanine transaminase [ALT]) and electrolytes (total calcium, chloride, potassium, sodium).

3. ECG will be done at baseline and prior to cycle 3. Additional ECG monitoring should be considered in patients who develop clinical significant electrolyte abnormalities during cisplatin therapy at the discretion of the treating physician.

4. Only in women of child bearing potential

5. If the genomic sample collection is missed at cycle 1 day 1, it can be collected at any time point during the study.

6. Every 4 months throughout years 1-2, then every 6 months for years 3-5.

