## 7.6 POST TREATMENT EVALUATIONS: ~30 days -60 days from last treatment

- Physical examination
- weight, BP
- ECOG performance
- Platelets, ANC, Hgb
- Complete metabolic profile (CMP) including: serum chemistries (creatinine, glucose, total protein, blood urea nitrogen [BUN], total carbon dioxide [CO2], albumin, total bilirubin, alkaline phosphatase, and aspartate transaminase [AST] and alanine transaminase [ALT]) and electrolytes (total calcium, chloride, potassium, sodium)
- Assessment of adverse events and concomitant medications

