## 7.7 FOLLOW-UP:

- Patients will be monitored by their treating physicians for the development of either local (chest wall, axillary, or supraclavicular nodes) or distal recurrent disease at least once every 4 months for the first two years, then at least every 6 months during years 3-5 after randomization.
- Suggested guidelines for surveillance of breast cancer survivors are available through the National Comprehensive Cancer Network ([www.nccn.org](http://www.nccn.org)).
- Routine blood work or radiology in the absence of symptoms suggestive of recurrent disease is not recommended.
- Remaining breast tissue (contralateral breast and ipsilateral breast in patients treated with breast conserving surgery) should be imaged annually according to standard screening guidelines.

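### Neuropathy first appearing on days 31-56 after the last cisplatin dose may go unrecorded in Arm A, depending on visit timing, while Arm B patients on maintenance are assessed throughout that period

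*Combined protocol and SAP*

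**What the plan says.** The protocol deals with this in several places.

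- **Recording period.** Section 11.2 says adverse events "will be recorded from the time of consent and for at least 30 days after treatment discontinuation". This is a minimum with no upper limit. The same section follows treatment-related events to resolution, but that applies to events already identified.
- **Post-treatment visit.** Section 7.6 is headed "POST TREATMENT EVALUATIONS: ~30 days -60 days from last treatment" and includes an adverse event assessment. The Arm A calendar in Section 7.0 gives the same window, "30-60 days from last treatment", and marks the adverse event row there. The row is blank under follow-up.
- **General rule.** Section 6.0 says patients leaving the treatment phase "will be evaluated at least 30 days after the last dose of study drug". It also says that adverse events of all grades are evaluated "at each study visit for the duration of their participation in the study".
- **Follow-up.** Section 7.7 has patients monitored for recurrence "at least once every 4 months for the first two years" and lists no adverse event assessment.
- **The harm.** Section 10.2.14 says "symptoms of neuropathy may begin 3 to 8 weeks after the last dose of cisplatin, although this is rare". The same sentence opens with "Although symptoms and signs of cisplatin neuropathy usually develop during treatment".
- **Arm B.** Under Section 5.2.2 (Tables 5 and 6), maintenance starts 3 weeks after Day 1 of the last combination cycle and lasts 24 weeks. Sections 7.3 and 7.4 require adverse event assessment every 4 weeks during it.

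**The concern.** The minimum recording period ends before the latest onset the protocol itself gives for a named cisplatin harm. In Arm A the last treatment is cisplatin on Day 1 of cycle 4, so the 30-day clock and the onset clock start together. In Arm B the 30-day clock starts only after maintenance, when the onset window has long closed.

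The first secondary objective is to characterise the side effects of cisplatin alone and of cisplatin with rucaparib. Section 12.5 tabulates safety by arm and allows Fisher's exact tests of selected events, without setting a common observation period. If the same cisplatin event can be recorded in one arm and missed in the other, part of any difference in neuropathy could come from how long patients were observed.

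**Working it through.** The plan gives no figure to reproduce on this point. The check compares calendar windows, counted in days from the last cisplatin dose.

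**Onset window (Section 10.2.14).** 3 × 7 = day 21 to 8 × 7 = day 56, a length of 56 − 21 = 35 days.

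**Arm A.** If recording of new events stops at a post-treatment visit on day d, the uncovered part is max(0, 56 − d) days.

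| Day recording stops | Uncovered days | Share of the 35-day window |
|---|---|---|
| 30 | 26 | 26/35 = 74% |
| 40 | 16 | 16/35 = 46% |
| 45 | 11 | 11/35 = 31% |
| 56 to 60 | 0 | 0% |

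Onsets on days 21-30 are always inside the minimum. Only days 31-56 are at risk.

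To turn calendar shares into shares of cases, I assume that onset is spread evenly over days 21-56 and visits evenly over days 30-60; neither assumption is in the documents. Coverage rises linearly from 9/35 = 26% at day 30 to 100% at day 56 and stays there to day 60. Average coverage is [26 × (0.257 + 1)/2 + 4 × 1]/30 = 0.68, so about 32% of late onsets would be missed.

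**A different reading of the clock.** If treatment discontinuation means the end of the last 21-day cycle, the minimum runs to day 21 + 30 = 51 and leaves 5 days uncovered. Sections 6.0 and 7.6 count from the last dose or last treatment, which favours the day-30 reading.

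**Arm B, maintenance completed.** The first maintenance dose is on day 21 and the 24th weekly dose on day 21 + 23 × 7 = 182. Recording runs to at least day 182 + 30 = 212. Four-weekly assessments counted from the first dose fall on about days 49 and 77, so the whole onset window is covered.

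**Possible number of cases.** Of 135 planned patients, 135 − 12 = 123 are left to randomise after the run-in, or about 61 in Arm A if allocation is 1:1 (the ratio is not stated). The late-onset rate is not given either, so 1% to 10% is an assumption for illustration.

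- All visits on day 30: 61 × 0.01 × 0.743 = 0.45 to 61 × 0.10 × 0.743 = 4.5 cases missed.
- Visits spread evenly over days 30-60: 61 × 0.01 × 0.32 = 0.2 to 61 × 0.10 × 0.32 = 2.0 cases missed.
- All visits on day 56 or later: none missed.

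**The case against.** The strongest reply is that nothing in the protocol says recording closes at day 30. Section 11.2 sets a floor, the post-treatment visit may fall as late as day 60, and Section 6.0 taken literally extends adverse event evaluation to the four-monthly follow-up visits. Since Section 10.2.14 says neuropathy may progress after treatment and may be irreversible in some patients, some late cases would still be evident then. Serious cases have a separate route: Section 11.3.1 asks sites to report any serious event during the study and sets no 30-day limit. Late onset is called rare, and the between-arm tests are optional and exploratory.

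Most of this stands, and it rules out stronger readings that a reader might infer:

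- *Late neuropathy goes unrecorded in the control arm.* The documents support only that it may, depending on the visit date and on which instruction the site follows.
- *About 60 Arm A patients are affected.* That is roughly the size of the arm. Only the rare patient with late onset could be affected.
- *A cisplatin effect will be mistaken for a rucaparib effect.* The direction of bias is plausible, but no rate in the documents shows that it would be large enough to mislead.
- *Every Arm B patient is covered.* Those who cannot start maintenance within 6 weeks stop protocol treatment and have the same short minimum as Arm A.

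The reply does not remove the gap. Section 6.0 conflicts with the blank follow-up cell in the Arm A calendar and with Section 7.7, which describes follow-up as monitoring for recurrence. A site working from the calendar and Section 11.2 complies with both and can still stop at day 30. The serious-event route leaves non-serious late onsets uncovered.

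**Conclusion.** The point holds in a limited form. Neuropathy starting on days 31-56 after the last cisplatin dose may be missed in Arm A, while Arm B patients on maintenance are assessed over those days. The uncovered part ranges from 26 of 35 days (visit on day 30) to none (visit on day 56 or later). This assumes that the clock starts at the last cisplatin dose and that sites follow the calendar rather than the broader sentence in Section 6.0.

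The number of missed cases cannot be derived from the documents. The illustrative range of 0 to about 4.5 rests on an assumed 1-10% rate and 1:1 allocation, and since the protocol calls late onset rare, the lower part is more plausible. The effect is confined to the secondary safety description and its exploratory comparison; DFS is unaffected. This is a minor point, worth correcting because the correction is cheap.

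**What to change.** Reconcile Sections 6.0, 7.6 and 11.2 and the Arm A calendar so that they give one instruction: new-onset neuropathy, with its onset date, is collected in both arms to at least 8 weeks after the last cisplatin dose. Use existing contacts: the post-treatment visit if it falls on day 56 or later, otherwise the first follow-up visit after that day. Leave the post-treatment visit and its laboratory tests where they are. Moving the visit to days 56-60 would also close the gap, but would delay the only scheduled post-treatment blood counts, chemistries and examination in Arm A.

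In Section 12.5, state that neuropathy is tabulated and compared by arm over a common period ending 8 weeks after the last cisplatin dose. Events beyond that period can be listed separately.

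The cost is amendment wording and one added adverse event item at an existing follow-up visit for some Arm A patients. Some onset dates will be recalled rather than observed, so cases near the 8-week boundary may be misplaced.
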